13.2 Sample Size, Accrual Rate and Study Duration

Based on the DFCI and MDACC experience, the accrual duration is projected to be 36 months to enroll a total of 45 patients who receive protocol therapy. Patients will be followed actively for 5 years or until disease progression or initiation of an alternative anti-cancer therapy and thereafter

for survival.

13.3 Randomization and Stratification Factors

Treatment assignment will be between the two arms will be stratified by the extent of disease:

- Resectable
- Borderline resectable

The biostatistics collaborator will generate and provide two separate randomization lists, with each list corresponding to one disease subtype, to be used for treatment assignment during the trial.

13.4 Interim Monitoring Plan

The DF/HCC Data and Safety Monitoring Board (DSMB) will review and monitor protocol progress and patient safety according to their standard schedule twice a year. Since all patients will receive standard of care therapy no formal plan will be implemented for interim analysis of primary and secondary endpoints. Additional safety monitoring plan is detailed in Section 13.7.1.

13.5 Analysis of Primary Endpoints

Patients' demographic and clinical characteristics will be summarized using descriptive statistics. Specifically, categorical covariates will be summarized by frequencies and percentages and their associations between groups will be assessed using the Chi Square test or Fisher's exact test. Continuous covariates will be summarized by means, standard deviations, medians and ranges, and the difference between groups will be assessed using the t-test or Wilcoxon rank sum test.

We will estimate the MPR for each arm. Due to the small sample size, we will estimate the MPR with its 95% exact confidence interval (CI). Among 30 patients treated in experimental arm, assuming 9 out of 30 patients have achieved primary endpoint, the 95% CI of MPR will be (0.15, 0.49). Additionally, generalized linear regression models will be explored to evaluate the

associations between the endpoint of MPR and covariates of interest.

13.6 Analysis of Secondary Endpoints

- Progression free survival time is defined as the time period from the date of randomization to the date of disease progression, recurrence after surgery or death from any cause whichever occurs first.
- The overall survival time is defined as the time duration from randomization till death or last follow-up if the patient is alive.

The distributions of overall survival and progression free survival will be estimated using the Kaplan-Meier method. Comparisons of these time-to-event endpoints by important covariate subgroups will be made using the log-rank tests. Cox proportional hazards regression models will be explored to evaluate the associations between the time-to-event endpoints and covariates of interest.

13.7 Reporting and Exclusions

13.7.1 Evaluation of Toxicity

All patients will be evaluable for toxicity from the first dose of protocol therapy.

For patient safety, a Bayesian toxicity monitoring rule will be implemented for the dose limiting toxicity (DLT) events that are at least possibly related to the investigational agent in the opinion of the investigators and occur within 28 days from the end of the drug administration according to Common Terminology Criteria for Adverse Events (CTCAE) v5.0. DLT events will include:

- Grade 3 or higher non-hematologic toxicity except:
 - Grade 3 fatigue
 - Grade 3 diarrhea or vomiting that lasts less than 72 hours
- Grade 4 or higher hematologic toxicity and:
 - Febrile neutropenia
 - Grade 4 neutropenia lasting longer than 7 days

Let p_{tox} be the toxicity probability at least possibly related to the investigational agent in the opinion of the investigators with a prior distribution of $\text{Beta}(0.33, 0.67)$, then if $\text{Pr} [p_{\text{tox}} > 0.33] > 0.7$, we will terminate the experimental arm early. Patients within the safety lead in cohort of the first 5 patients will be monitored for DLT at least possibly related to investigational agent. Based on these assumptions and monitoring conditions, we will early stop the study if we observe $[\# \text{ patients experiencing toxicity}] / [\# \text{patients being treated}] \geq 3/5$ DLTs in the safety lead in cohort. The operating characteristics are shown in Table 2.

Table 2. Operating characteristics for toxicity monitoring

True toxicity probability	Early stopping probability	Average sample size
0.1	0.010	29.8
0.2	0.093	28.0
0.3	0.354	23.4
0.4	0.710	16.7
0.5	0.931	11.0

The toxicity boundaries and operating characteristics were generated using web-based applications available at <https://trialdesign.org>.

Safety data analysis: Toxicity severity and grade data will be summarized with descriptive statistics overall and by treatment arms.

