efficacy on interim analysis. There were no dose limiting toxicities attributed to NIS793 in this trial. The second trial is a phase II randomized, open label, parallel arm study of NIS793 (with and without spartalizumab) in combination with SOC chemotherapy gemcitabine/nab-paclitaxel, and SOC alone in first-line metastatic pancreatic ductal adenocarcinoma (mPDAC). As of 26-Mar-2021, nine patients have been enrolled and treated in safety run-in part with NIS793 2100 mg Q2W and spartalizumab 400 mg Q4W in combination with gemcitabine 1000 mg/m² Days 1, 8 and 15 and nab-paclitaxel 125 mg/m² Days 1, 8 and 15. Out of nine patients, one patient (11.1%) experienced a DLT grade 3 colitis.

For complete information regarding dosing, pharmacokinetics, pharmacodynamics and updated safety information please refer to the most updated Investigator's Brochure. NIS793 has not been combined with FOLFIRINOX or radiation in clinical trials thus far.

2.3 *Modified FOLFIRINOX (fluorouracil, leucovorin, oxaliplatin, irinotecan)*

mFOLFIRINOX (fluorouracil, leucovorin, oxaliplatin, irinotecan) will be administered as neoadjuvant chemotherapy for resectable or borderline resectable disease per institutional standards. mFOLFIRINOX is a chemotherapy regimen comprised of 5-fluorouracil, leucovorin, oxaliplatin and irinotecan. Dosing of these medications is as follows: *Fluorouracil 2400 mg/m², Leucovorin 400 mg/m², Irinotecan 150 mg/m², Oxaliplatin 85 mg/m²*. mFOLFIRINOX has been extensively studied and characterized for the treatment of pancreatic and other cancers. It is a preferred regimen for the neoadjuvant treatment of resectable or borderline resectable pancreatic cancer per NCCN guidelines(14-16). For metastatic pancreatic cancer and for adjuvant therapy, it is a category 1 recommended regimen by NCCN guidelines, and it is also a preferred regimen for locally advanced disease.

For a comprehensive list of side effects and toxicities, please refer to the FDA label for the individual agents.

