12.2 Data Safety Monitoring

The DF/HCC Data and Safety Monitoring Board (DSMB) will review and monitor study progress, toxicity, safety and other data from this study. The Board is chaired by a medical oncologist from outside of DF/HCC and its membership composed of internal and external institutional representation. Information that raises any questions about participant safety or protocol performance will be addressed by the Sponsor-Investigator, statistician and study team. Should any major concerns arise, the DSMB will offer recommendations regarding whether or not to suspend the study.

The DSMB will meet twice a year to review accrual, toxicity, response and reporting information. Information to be provided to the DSMB may include: participant accrual; treatment regimen information; all adverse events and serious adverse events reported across all sites by category; summary of any deaths on study; audit results; and a summary provided by the study team. Other information (e.g. scans, laboratory values) will be provided upon request.

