Eligible patients with newly diagnosed resectable or borderline resectable pancreatic adenocarcinoma will be randomly assigned in a 2:1 allocation ratio to one of the two interventions: NIS793 and FOLFIRINOX chemotherapy for 8 cycles (Arm A, Experimental arm) followed by surgery, or FOLFIRINOX for 8 cycles (Arm B, Control arm) followed by surgery. The experimental (Arm A) and control arms (Arm B) will accrue 30 and 15 patients respectively. The first five patients randomized to NIS793 (Arm A) will be part of a safety lead-in. Study will pause until the last patient accrued for safety lead-in has completed two full treatment cycles (i.e., 28 days). Participants must have received at least 75% of their assigned doses of FOLFIRINOX and NIS793 to be considered evaluable for this safety analysis, unless dosing was held or reduced due to toxicity. If one or more of the first five participants enrolled does not meet this parameter for a reason other than toxicity (e.g. rapid disease progression and subsequent removal), Arm A will continue to accrue as many participants as needed to have five evaluable participants for safety assessment. Patients with borderline resectable pancreatic adenocarcinoma will receive chemoradiation after completion of systemic chemotherapy prior to surgery. As per the standard of care, the time interval between completion of neoadjuvant chemotherapy and radiation will be 2-4 weeks for patients with borderline resectable pancreatic adenocarcinoma and the interval between completion of neoadjuvant treatment and surgery for all patients will be between 2-8 weeks.

We will compare experimental arm to the control arm to see if it has improved the major pathological response rate (MPR). The experimental treatment will be claimed to be successful if

$\Pr(p.e > p.c + 0.05 | \text{data}) > \theta_t$, where $p.e$ and $p.c$ are the MPR for the experimental arm and control arm, respectively, and θ_t is the threshold value. We assume the prior distributions $p.e \sim \text{Beta}(0.3, 0.7)$ and $p.c \sim \text{Beta}(0.13, 0.87)$, which reflect that the expected MPR being 30% in experimental arm and 13% in control arm.

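### The one printed toxicity boundary (3 or more of 5) cannot produce Table 2, and the later looks that would are not written

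*Combined protocol and SAP*

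**What the plan says.** Section 13.7.1 places a Beta(0.33, 0.67) prior on the DLT probability and closes the experimental arm if the posterior probability that it exceeds 0.33 is above 0.7. No look times accompany the criterion. The text continues: "we will terminate the experimental arm early. Patients within the safety lead in cohort of the first 5 patients will be monitored for DLT". It then derives one stopping count, 3 or more DLTs among those 5 patients, and goes straight on to the table: "DLTs in the safety lead in cohort. The operating characteristics are shown in Table 2".

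Two statements in the same section suggest wider monitoring: "All patients will be evaluable for toxicity from the first dose of protocol therapy", and, below the table, "The toxicity boundaries and operating characteristics were generated using web-based applications", where boundaries is plural.

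Elsewhere, Section 13.1 and note D of the Section 10 calendar describe one accrual pause, after the lead-in. Section 13.4 mentions the twice-yearly DSMB review and otherwise refers back: "Additional safety monitoring plan is detailed in Section 13.7.1". Section 12.2 says "The DSMB will meet twice a year to review accrual, toxicity, response and reporting information", without linking those meetings to the criterion.

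**The concern.** The wording a site or the DSMB would act on describes one look at 5 patients. Table 2 shows an arm with a true DLT rate of 0.5 being stopped 93% of the time, which is far more than one look at 5 patients can deliver. Either the table belongs to a different rule, or further looks are intended and unstated.

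This is the plan's statistical rule for closing the arm on toxicity, and Section 2.2 says "NIS793 has not been combined with FOLFIRINOX or radiation in clinical trials thus far". Anyone who judges the safety design by Table 2 may be crediting it with protection that the operational text does not secure.

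**Working it through.** **Inputs.** Prior Beta(0.33, 0.67), criterion Pr(p > 0.33 | data) > 0.7, printed boundary 3/5 and Table 2 are from Section 13.7.1. The Arm A maximum of 30 is from Section 13.1. Look times after patient 5 are not given, so each schedule below is an assumption.

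**1. Is 3/5 right for the criterion?** After k DLTs in n patients the posterior is Beta(0.33 + k, 0.67 + n − k). At n = 5, Pr(p > 0.33) is 0.589 for k = 2 and 0.868 for k = 3. The boundary is correct, so a wrong boundary does not explain the gap.

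**2. Reproducing Table 2.** The smallest k that meets the criterion at later multiples of 5 is:

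- 5/10 (posterior 0.848)
- 7/15 (0.849)
- 8/20 (0.726)
- 10/25 (0.753)

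An exact binomial recursion carries forward the DLT counts below each boundary, adds 5 patients, and removes the probability at or above the next boundary. At rate 0.4 the stopping probabilities at the five looks are 0.3174, 0.1331, 0.0772, 0.1365 and 0.0458, which sum to 0.710. Average size is 5(0.3174) + 10(0.1331) + 15(0.0772) + 20(0.1365) + 25(0.0458) + 30(0.2900) = 16.65. Both agree with the table, as do the entries at the other four rates.

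**3. The printed boundary alone.** Stopping probability s = 10p³(1−p)² + 5p⁴(1−p) + p⁵, and average size = 5s + 30(1−s). At p = 0.4, s = 0.2304 + 0.0768 + 0.0102 = 0.317 and average size is 22.1.

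| True rate | Stop, look at 5 only | Stop, Table 2 | Ratio | Average n, look at 5 only | Average n, Table 2 |
|---|---|---|---|---|---|
| 0.1 | 0.009 | 0.010 | about 1 | 29.8 | 29.8 |
| 0.2 | 0.058 | 0.093 | 1.6 | 28.6 | 28.0 |
| 0.3 | 0.163 | 0.354 | 2.2 | 25.9 | 23.4 |
| 0.4 | 0.317 | 0.710 | 2.2 | 22.1 | 16.7 |
| 0.5 | 0.500 | 0.931 | 1.9 | 17.5 | 11.0 |

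The stopping probability of a single look at 5 does not depend on the maximum sample size, so no choice of maximum closes the gap.

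**4. How much of Table 2 comes from unwritten looks?** The share is (five-look − one-look) / five-look. At 0.4 it is (0.710 − 0.317)/0.710 = 55%. At 0.2, 0.3 and 0.5 it is 38%, 54% and 46%.

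**5. Sensitivity to look times, true rate 0.4.**

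| Looks at | Stop |
|---|---|
| 5 only | 0.317 |
| 5, 15, 25 | 0.663 |
| 5, 10, 15, 20, 25 | 0.710 |
| the same plus 30 | 0.740 |
| every patient, 5 to 29 | 0.805 |

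Among schedules starting at 5 with equal steps of 1 to 25 patients, ending by 29 or by 30, only steps of 5 ending at 25 match all ten entries. Looks at 5, 14 and 23 come close on stopping (0.705 at 0.4, 0.926 at 0.5) but give average sizes of 17.05 and 11.65 where Table 2 has 16.7 and 11.0.

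**The case against.** The strongest reply is that this is an omission and not a contradiction. The posterior criterion is itself part of the text, it defines a boundary at any n, and with looks every 5 patients it yields Table 2 exactly. On that view 3/5 is the criterion worked out for the first cohort. The statement that all patients are evaluable, the plural reference to boundaries and Table 2 itself all favor continued monitoring. A pause in accrual after the lead-in does not rule out later looks without a pause. The twofold overstatement would then arise only if the sponsor ignored its own criterion after patient 5. DSMB review and the patient-level NIS793 hold and discontinuation rules in Section 6.2 also remain in force.

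Much of this stands. Table 2 is correctly calculated for one schedule, continued monitoring is a fair reading, and the lead-in-only figures are conditional on the other reading. But the plan does not settle which reading applies. The only monitored group named and the only count printed both concern 5 patients. Even on the favorable reading, the schedule has to be recovered by calculation, and other reasonable continued schedules miss Table 2. Neither DSMB section says the criterion is applied at its meetings, and patient-level rules do not decide whether the arm closes.

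**Conclusion.** The concern holds and should be fixed. Table 2 reports properties that the printed boundary does not have.

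- **If only 3/5 is applied:** Table 2 overstates stopping by a factor of 1.6 at a true rate of 0.2 and by 1.9 to 2.2 at 0.3 to 0.5, with little difference at 0.1. The arm would reach 30 patients with probability 0.683 (1 − 0.317) where Table 2 implies 0.290 (1 − 0.710) at rate 0.4, and 0.500 where it implies 0.069 at rate 0.5.
- **If the criterion continues every 5 patients to 25:** Table 2 is right, but four of its five looks are unwritten.

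These figures assume independent patients with a constant DLT rate, DLT status known at each look, a maximum of 30, and no closure of the arm by the DSMB or for other reasons. The every-5 schedule is inferred from the match and is not stated in the plan.

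**What to change.** Reconcile the text of Section 13.7.1 with Table 2. The sponsor should state whether the posterior criterion is applied after the lead-in. If it is, the section should list the numbers of treated Arm A patients at which it is checked, the boundary at each, and who checks it. Table 2 should then show the operating characteristics of the rule actually to be used.

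For reference only, without preferring either: looks at 5, 10, 15, 20 and 25 leave Table 2 as it is, and a look at 5 only would replace it with the lead-in-only figures tabulated above. The choice is the sponsor's.

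The same paragraph speaks of ending the experimental arm in one sentence and of stopping the study in another. These should be reconciled in the same edit.

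The cost is a few lines or one small table, with no extra patients.

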13.7.2 Evaluation of the Primary Efficacy Endpoint

Major pathologic response will be analyzed according to modified intent-to-treat, excluding patients determined to be ineligible at randomization or who withdraw consent prior to starting any protocol therapy.

APPENDIX A PERFORMANCE STATUS CRITERIA

ECOG Performance Status Scale		Karnofsky Performance Scale	
Grade	Descriptions	Percent	Description
0	Normal activity. Fully active, able to carry on all pre-disease performance without restriction.	100	Normal, no complaints, no evidence of disease.
		90	Able to carry on normal activity; minor signs or symptoms of disease.
1	Symptoms, but ambulatory. Restricted in physically strenuous activity, but ambulatory and able to carry out work of a light or sedentary nature (e.g., light housework, office work).	80	Normal activity with effort; some signs or symptoms of disease.
		70	Cares for self, unable to carry on normal activity or to do active work.
2	In bed <50% of the time. Ambulatory and capable of all self-care, but unable to carry out any work activities. Up and about more than 50% of waking hours.	60	Requires occasional assistance, but is able to care for most of his/her needs.
		50	Requires considerable assistance and frequent medical care.
3	In bed >50% of the time. Capable of only limited self-care, confined to bed or chair more than 50% of waking hours.	40	Disabled, requires special care and assistance.
		30	Severely disabled, hospitalization indicated. Death not imminent.
4	100% bedridden. Completely disabled. Cannot carry on any self-care. Totally confined to bed or chair.	20	Very sick, hospitalization indicated. Death not imminent.
		10	Moribund, fatal processes progressing rapidly.
5	Dead.	0	Dead.

NCI Protocol #: NCT05546411

Version Date: 03/13/2023

DF/HCC Protocol #: 22-314

1. INTRODUCTION

The Dana-Farber/Harvard Cancer Center Multi-Center Data and Safety Monitoring Plan (DF/HCC DSMP) outlines the procedures for conducting a DF/HCC Multi-Center research protocol. The DF/HCC DSMP serves as a reference for any sites external to DF/HCC that are participating in a DF/HCC clinical trial.

1.1. Purpose

To establish standards that will ensure that a Dana-Farber/Harvard Cancer Center Multi-Center protocol will comply with Federal Regulations, Health Insurance Portability and Accountability Act (HIPAA) requirements and applicable DF/HCC Policies and Operations.

2. GENERAL ROLES AND RESPONSIBILITIES

For DF/HCC Multi-Center Protocols, the following general responsibilities apply, in addition to those outlined in DF/HCC Policies for Sponsor-Investigators:

2.1. External Site

An External Site is an institution that is outside the DF/HCC and DF/PCC consortium that is collaborating with DF/HCC on a protocol where the sponsor is a DF/HCC investigator. The External Site acknowledges the DF/HCC Sponsor as having the ultimate authority and responsibility for the overall conduct of the study.

Each External Site is expected to comply with all applicable DF/HCC requirements stated within this Data and Safety Monitoring Plan and/or the protocol document..

The general responsibilities for each External Site may include but are not limited to:

- Document the delegation of research specific activities to study personnel.
- Commit to the accrual of participants to the protocol.
- Submit protocol and/or amendments to their IRB of record. For studies under a single IRB, the Coordinating Center will facilitate any study-wide submissions..
- Maintain regulatory files as per ICH GCP and federal requirements.
- Provide the Coordinating Center with regulatory documents or source documents as requested.
- Participate in protocol training prior to enrolling participants and throughout the trial as required.
- Update Coordinating Center with research staff changes on a timely basis.
- Register participants through the Coordinating Center prior to beginning research related activities when required by the sponsor.
- Submit Serious Adverse Event (SAE) reports to sponsor, Coordinating Center, and IRB of record as applicable, in accordance with DF/HCC requirements.

- Submit protocol deviations and violations to the Sponsor, Coordinating Center, and IRB of record as applicable..
- Order, store and dispense investigational agents and/or other protocol mandated drugs per federal guidelines and protocol requirements.
- Participate in any quality assurance activities and meet with monitors or auditors at the conclusion of a visit to review findings.
- Promptly provide follow-up and/or corrective action plans for any monitoring queries or audit findings.
- Notify the sponsor immediately of any regulatory authority inspection of this protocol at the External Site.

3. DF/HCC REQUIREMENTS FOR MULTI-CENTER PROTOCOLS

Certain DF/HCC Policy requirements apply to External Sites participating in DF/HCC research. The following section will clarify DF/HCC requirements and further detail the expectations for participating in a DF/HCC Multi-Center protocol.

3.1. Protocol Revisions and Closures

The External Sites will receive notification of protocol revisions and closures from the Coordinating Center. When under a separate IRB, it is the individual External Site's responsibility to notify its IRB of these revisions.

- **Protocol revisions:** External Sites will receive written notification of protocol revisions from the Coordinating Center. All protocol revisions should be IRB approved and implemented within a timely manner from receipt of the notification.
- **Protocol closures and temporary holds:** External Sites will receive notification of protocol closures and temporary holds from the Coordinating Center. Closures and holds will be effective immediately. In addition, the Coordinating Center, will update the External Sites on an ongoing basis about protocol accrual data so that they will be aware of imminent protocol closures.

3.2. Informed Consent Requirements

The DF/HCC approved informed consent document will serve as a template for the informed consent for External Sites. The External Site consent form must follow the consent template as closely as possible and should adhere to specifications outlined in the DF/HCC Guidance Document on Model Consent Language for Investigator-Sponsored Multi-Center Trials. This document will be provided separately to each External Site upon request.

External Sites must send their version of the informed consent document to the Coordinating Center for sponsor review and approval. If the HIPAA authorization is a separate document, please submit to the sponsor for the study record. Once sponsor approval is obtained, the External site may submit to their IRB of record, as applicable. In

these cases, the approved consent form must also be submitted to the Coordinating Center after approval by the local IRB for all consent versions.

The Principal Investigator (PI) at each External Site will identify the appropriate members of the study team who will be obtaining consent and signing the consent form for protocols. External Sites must follow the DF/HCC requirement that for all interventional drug, biologic, or device research, only attending physicians may obtain initial informed consent and any re-consent that requires a full revised consent form.

